In the last few years, the observed increase in costs has been posing major challenges for the healthcare system. Healthcare costs in Switzerland have risen by a good third within the last decade (10). As one way to reduce costs and simultaneously improve quality of care, hospital readmissions receive increasing interest from policy makers. It is only relatively recently that policies were developed with the specific aim of reducing readmissions. In Switzerland, the readmission policy involves financial penalties, i.e., that patient records of the first admission and the relevant readmission are merged into a single case, if certain criteria are met. Consequently, hospitals receive only one DRG-based payment for both admissions (11). In result, and despite the fact that some readmissions cannot be avoided and the proportion of potentially avoidable readmissions (PARAs) remains debatable, health care organizations invest considerable resources into efforts to reduce hospital readmissions (12-14).

To most efficiently reduce readmissions, hospitals need to target effective discharge and postdischarge interventions at those who need them the most. One of the more recent strategies is the application of prediction models. As systematic reviews have shown, there are many models aimed at identifying those at greater risk of readmission (15, 16). The majority includes readily available predictors such as demographic and administrative data, comorbidities, laboratory, and medications (15). Among these models, the EPIC's Risk of Unplanned Readmission model, developed in 2015 for the U.S. acute care hospital setting, promises superior calibration and discriminatory abilities. The model was developed by EPIC Systems corporation based on data from 26 EPIC community member hospitals, including more than 275'000 inpatient hospital admission encounters to determine a patient's risk of unplanned readmission within 30 days of being discharged from an index admission.

RATIONALE & OBJECTIVES

Prediction models require internal and external validation. Whereas internal validations means testing the model in the population used to develop it, external validation means applying the model with its predictors and assigned weights, as estimated from the development study, to a new population; measuring the predictor and outcome values; and quantifying the model's predictive performance (calibration and discrimination).

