Backward feature selection was performed (with a significance level of $\alpha = 0.05$) and resulted in 11 significant covariates. The final point score ranges from -15 to 114, a score greater than 90 is considered with a high risk for unplanned readmission or death within 30 days after discharge. The internal validation of the 11-item index, excluding the Canada specific case-mix group (CMG) score,

showed reasonable discrimination with an AUC of the ROC curve of 0.743 for all-cause unplanned readmission, but poor calibration (H – L statistic 58.93, p < 0.0001).

SQLape®: The SQLape® readmission risk model (Striving for Quality Level and analyzing of patient expenditures), a computerized validated algorithm, was developed in 2002, in Switzerland (6). The SQLape® prediction model predicts unforeseen hospital readmission within 30 days after hospital discharge. The development sample consisted of 131'809 inpatient stays from 49 Swiss acute care hospitals, of which 12 hospitals were located in the French speaking part of Switzerland.

Healthy newborns, residents outside of Switzerland and elective surgical patients that could usually be performed as day surgery were excluded. After backward elimination was performed, the Poisson regression model consisted of six variables/SQLape variable groups. Of the beforementioned 131'809 inpatient stays, 66'069 were used for internal validation. The discrimination was measured by the Harrell's C statistic, which is also referred to as the estimated area under the Receiver Operating Characteristics (ROC) curve (AUC). A value of 0.72 showed reasonable discriminative ability.

Outcome(s)

The predicted outcome of all prediction models will be compared with the observed outcome. Both outcomes will be assessed retrospectively. The primary outcome will be the all-cause unplanned readmission to the same hospital within 30 days after the index hospital discharge. An unplanned readmission will be defined as an urgent readmission, i.e. not scheduled in advance and requires treatment within 12 hours.

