The secondary outcome, as defined by the SwissDRG, will be the unplanned readmission to the same hospital, that resulted in a case merging (19). According to SwissDRG, patient records of the index admission and the nth readmission are merged into a single case if they fall into the same major diagnostic category (MDC), occurred within 18 days after the index/preceding hospital discharge date, and are not excluded from the case merging rule.

Sample size

Sample size calculations resulted in a aspired sample size of at least 1000 participants (500 cases and 500 controls) for each site. The proposed sample size is based upon precision. 500 cases and 500 controls will ensure that the half-width of a 95% confidence interval for sensitivity and specificity (using frequencies of predicted vs. actual outcome) does not exceed 5%; even for a point estimate of 50%, leading to the widest possible confidence interval, the half-width is supposed to remain slightly below 4.5%. This can be considered to be an appropriate target precision for the purpose of this study.

Data collection

Demographic and administrative data, medications, orders, International Classification of Disease (ICD) diagnosis codes, and biological data will be extracted in an anonymized manner from electronic patient records. Data covering the initial period will be retrieved from several different Information Systems (e.g. Dorner Lab. System, NEXUS/Medfolio etc.). Because of the introduction of a new Clinical Information System (CIS) in 2019, data covering the latter period of interest (23rd of September to 31st of December 2019) will be retrieved separately, i.e., from the new Clinical Information System from EPIC Systems corporation.

Missing data

Missing data required to compute the prediction models will be handled as following: Missing biological data (hemoglobin, sodium, calcium etc.) will be coded as normal values. Missing comorbidity and medication data will be considered as absence of the condition and no active medication, respectively. Missing order data (imaging, restraining, electrocardiogram) will be considered as an intervention not ordered. Lastly, missing records of utilization of health care resources (e.g. ED visits, scheduled future admissions etc.) will be considered as non-utilization.

Missing demographic or administrative data to describe patient's characteristics will result in the patient's exclusion from the analysis.

Statistical analysis

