The EPIC's Risk of Unplanned Readmission model predictions and LACE+ scores will be calculated as the inverse of $1+e^{-(intercept+\beta^{1_*}x^1+\dots+\beta^{K_*}x^K)}$, where β will be the regression coefficient of each covariate (x), and K will be the total number of covariates. SQLape[®] readmission predictions will be automatically calculated by the plugin provided by the author.

To assess the performance, the traditional statistical approach is to quantify how close predictions are to the actual outcome. As overall performance measure, composing of discrimination and calibration, the Brier score will be calculated. Assessed separately, the discriminative ability will be measured using the Harrell's C-statistic, which, for binary outcomes, is identical to the area under the Receiver Operating Characteristic (ROC) curve (AUC). For calibration, the Hosmer-Lemeshow goodness-of-fit test will be graphically illustrated by plotting the predicted outcomes by decile against the observations. Furthermore, other performance measures to be estimated will include the Net Reclassification Improvement (NRI) and the Net Benefit (NB). All statistical analyses will be performed in R.

Risk groups

Risk groups will be established based on the recommendations by the developers of EPIC's Risk of Unplanned Readmission model, i.e., to use the organization's current readmission rate as baseline

risk and group as follows: "no risk = 0 – baseline", "low risk = baseline – 2 x baseline", "medium risk = 2 x baseline – 3 x baseline", "high risk = > 3 x baseline".

Development vs. validation

The differences in this validation study compared to the development studies are briefly summarized below:

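### The Hosmer-Lemeshow test is named for predictions fixed in advance without a reference distribution; in its usual 8-df form at an assumed 5% level it would reject a perfectly calibrated model about 11.5% of the time

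*Combined protocol and SAP*

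**What the plan says.** The calibration method is given in one sentence of METHODS, Statistical analysis, which the ABSTRACT repeats: "For calibration, the Hosmer-Lemeshow goodness-of-fit test will be graphically illustrated by plotting the predicted outcomes by decile against the observations". Neither place gives degrees of freedom, a significance level or a rule for reading the result.

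That the predictions are fixed in advance follows from two places. RATIONALE & OBJECTIVES says that "external validation means applying the model with its predictors and assigned weights, as estimated from the development study, to a new population". Statistical analysis computes the EPIC and LACE+ predictions from a logistic formula with given coefficients, and says of SQLape that "readmission predictions will be automatically calculated by the plugin provided by the author". No section plans to refit or recalibrate a model on the study outcomes. The changes to diagnosis and medication groupers listed under Development vs. validation alter how inputs are coded, not the weights.

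Under Predictors, the LACE+ paragraph reports that index's own internal validation as showing reasonable discrimination "but poor calibration (H – L statistic 58.93, p < 0.0001").

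**The concern.** A goodness-of-fit statistic is only as good as the distribution it is compared with. The familiar decile version of this test subtracts two degrees of freedom because the model's coefficients have been estimated from the patients being tested, which pulls observed and expected counts together. Its null hypothesis is that a model fitted to these patients has the right form. The question here is different: do predictions fixed elsewhere agree with outcomes in new patients? Nothing has been fitted, so nothing should be subtracted.

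Rationale & objectives names calibration as one of the two components of predictive performance, and this is the only calibration-specific test in the plan; the Brier score mixes calibration with discrimination. An analyst who runs the named test in its usual form would get p-values that are too small, always to the disadvantage of the model.

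**Working it through.** **The plan's own figure.** The plan gives no error rate for this test. Its only statistical calculation is in Sample size, which concerns "the half-width of a 95% confidence interval for sensitivity and specificity". With 500 per group and a 50% estimate, 1.96 × √(0.25/500) = 4.38%, which agrees with the stated value of slightly below 4.5%. It has no bearing on the calibration test.

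**Inputs.**
- Groups: 10, from the deciles in Statistical analysis.
- Coefficients estimated in the validation data: none, from Rationale & objectives and Statistical analysis.
- Reference distribution: not stated. Assumed to be the usual 10 − 2 = 8 df.
- Significance level: not stated. Assumed 5%, with 1% and 10% shown as a range.

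**Theory.** The statistic is the sum over groups of (O − E)² / [E(1 − E/n)], where O and E are the observed and expected readmissions and n the patients in the group. For fixed, correct predictions each of the ten terms is approximately an independent chi-square with 1 df, so the sum has about 10 df.
- 5% critical values: 15.51 (8 df) and 18.31 (10 df).
- P(chi-square with 10 df > 15.51) = 0.1146, or 11.5%, which is 0.1146 / 0.05 = 2.3 times nominal.
- At a nominal 1% the true rate is 2.8%; at a nominal 10% it is 20.4%.
- Example: a statistic of 16 gives p = 0.042 on 8 df and p = 0.100 on 10 df.

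**Simulation.** True risks came from a logistic model with three independent standard normal predictors, each with coefficient 0.5. Event rates were about 10% and 5% and AUC about 0.72 to 0.73. There were 6,000 replicates (3,000 at N = 20,000), and 1,500 for the refitted models. The event rates and N are assumptions; the plan does not give the hospital's own readmission rate or the expected number of eligible patients. Rejection rates at a nominal 5%:

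| N | Event rate | Fixed, 8 df | Fixed, 10 df | Refitted to same data, 8 df |
|---|---|---|---|---|
| 1,000 | 10% | 11.5% | 5.2% | 4.7% |
| 5,000 | 10% | 11.1% | 5.2% | 5.8% |
| 20,000 | 10% | 11.0% | 4.5% | 5.0% |
| 1,000 | 5% | 11.2% | 5.9% | 5.7% |
| 5,000 | 5% | 11.9% | 5.5% | 5.4% |

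The last column confirms that 8 df is right for a model fitted to the same patients. The two columns before it show that 10 df is right for fixed predictions.

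**When the model really is miscalibrated.** Predictions had mean risk 10% and a standard deviation of 0.9 on the logit scale, with true risk 20% below predicted (an assumption). Rejection on 8 df against 10 df was roughly 30% against 14% at N = 1,000, 98% against 95 to 97% at N = 5,000, and 100% against 100% at N = 10,000 and 20,000.

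**The LACE+ value.** A statistic of 58.93 gives p of about 8 × 10⁻¹⁰ on 8 df and 6 × 10⁻⁹ on 10 df. That verdict does not depend on the choice.

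**The case against.** The strongest reply is that the error is assumed, not found. The plan never mentions 8 df, and an analyst who used 10 df would comply with every word of it. The sentence commits to a plot, which does not depend on df, and no conclusion, model choice or sample size in the plan hangs on a Hosmer-Lemeshow p-value. This largely stands and limits the point to a conditional one. What remains is that the plan names a goodness-of-fit test, not merely a plot, in a setting where its usual form is invalid, and states no adaptation.

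The second reply is that the models are unlikely to be perfectly calibrated here. The secondary outcome is an 18-day case merging within the same diagnostic category, while the models predict 30-day outcomes. LACE+ was developed for death or urgent readmission. SQLape was developed for potentially avoidable readmissions. Only readmissions to the same hospital count. This also stands: once miscalibration is material and the sample is large, the choice of df changes almost nothing.

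Three stronger readings are tempting and are not supported:
- A reader might infer that every reported p-value will be too small. That would need the plan to specify 8 df, and it does not.
- A reader might compound the 11.5% over three models and two outcomes into a large chance of some false rejection. That needs six true nulls and six independent tests. The mismatches above make the first implausible, and shared patients with overlapping outcomes rule out the second.
- A reader might take the LACE+ sentence as this study's decision rule. It reports another study's internal validation.

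**Conclusion.** The point holds in conditional form and is minor. The plan applies the decile Hosmer-Lemeshow test to externally fixed predictions and leaves its reference distribution open. If the usual 8 df and a 5% level are used, a perfectly calibrated model is rejected about 11.5% of the time instead of 5%. The practical consequence is confined to a nearly calibrated model whose statistic falls between 15.51 and 18.31. The 11.5% rests on ten groups, no re-estimation on the study data, and the two assumed defaults; it hardly depends on event rate or sample size over the ranges simulated.

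**What to change.** Add to Statistical analysis that, because no coefficient is estimated in the validation data, the statistic for each externally fixed model and outcome is referred to chi-square with df equal to the number of groups (10 for deciles). Set this explicitly in the R code. Report the statistic, the number of groups and the df with each decile plot. If a model is recalibrated on the study data, use reduced df for that analysis only.

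This takes a sentence or two of text and one line of code, with no new data. The price is lower power to flag miscalibration: slight in large samples, but not negligible near the stated minimum of 1,000 patients, as the N = 1,000 figures above show. Calibration intercept and slope with confidence intervals would usefully show the direction and size of any miscalibration, but they would not correct the p-value of the test that the plan names.

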Even though EPIC's Risk of Unplanned Readmission model was developed for the acute care hospital setting, variations in demographic features, disease prevalence and differences in test conditions (e.g. defining criteria of relevant readmissions, time frame of measurement) entail external validation prior to routine application in the Swiss acute care hospital setting.

For this reason, the main objective of this study is to externally validate EPIC's Risk of Unplanned Readmission model as i) a predictor of all-cause unplanned hospital readmissions within 30 days, ii) a predictor of unplanned readmissions within 18 days according to SwissDRG's specification, and to compare the model with the LACE+ index and the SQLape® readmission algorithm.

METHODS

Study design & study sites

This monocentric, retrospective, diagnostic cohort study will include all inpatients from the Lucerne Cantonal Hospital, which is the largest provider of basic and highly specialized healthcare services in Central Switzerland. This study is designed not to meet the criteria for research involving human subjects. The Ethics Committee Northwest- and Central Switzerland (EKNZ) will be informed and asked for an ethics waiver.

Participants

All inpatients, aged one year or older (max. 100 years), who were hospitalized either between the 1st of January 2018 and the 31st of December 2018, or between the 23rd of September and the 31st of December 2019 will be included. Cases will be inpatients that experienced (i) an unplanned readmission within 18 days according to SwissDRG's specifications; (ii) an unplanned all-cause readmission within 30 days after the index discharge. The control group will consist of individuals who had no unplanned readmission within the relevant days after the index discharge.

Exclusion criteria will be (a) admission/transfer from another psychiatric, rehabilitative or acute care ward from the same institution, (b) discharge destination other than the patient's home or (c) transfer to another acute care hospital, both being considered as treatment continuation; (d) foreign residence, (e) deceased before discharge, (f) discharged on admission day, (g) refusal of general consent, and (h) unknown patient residence or discharge destination.

For individuals with multiple readmissions during the study period, only the first readmission will be included into the analysis.

Predictors

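### Calibration is not quantified by O/E, intercept or slope, and the Brier and Net Benefit comparison of the three models has no version with average mis-scaling removed

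*Combined protocol and SAP*

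**What the plan says.** Under Rationale & Objectives, external validation means "applying the model with its predictors and assigned weights, as estimated from the development study, to a new population" and then quantifying the model's "predictive performance (calibration and discrimination"). EPIC is to be validated for 30-day all-cause unplanned readmission and as "ii) a predictor of unplanned readmissions within 18 days according to" the SwissDRG rules, and is to be compared with LACE+ and SQLape.

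Under Statistical analysis, EPIC and LACE+ predictions come from the logistic formula; for SQLape, "readmission predictions will be automatically calculated by the plugin provided by the author". The measures are:
- Overall: "As overall performance measure, composing of discrimination and calibration, the Brier score will be calculated".
- Discrimination: the C-statistic (AUC).
- Calibration: "For calibration, the Hosmer-Lemeshow goodness-of-fit test will be graphically illustrated by plotting the predicted outcomes by decile against the observations".
- Further: "Furthermore, other performance measures to be estimated will include the Net Reclassification Improvement (NRI) and the Net Benefit (NB").

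Under Risk groups: "Risk groups will be established based on the recommendations by the developers" of EPIC. The cut-offs are one, two and three times the hospital's current readmission rate; the section does not say which outcome sets that rate.

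The protocol plans no O/E ratio, calibration intercept, calibration slope or comparison after updating. The only model changes it foresees are to the diagnosis and ATC groupers (Development vs. validation).

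**The concern.** Discrimination gets a number; calibration gets a test and a picture. Brier and Net Benefit both move when all of a model's predictions are too high or too low on average, even if its ranking of patients is unchanged. The protocol itself gives reasons to expect such shifts:
- The targets differ. EPIC predicts all-cause unplanned 30-day readmission; LACE+ was developed for 30-day death or urgent readmission. SQLape is described in two ways: unforeseen readmission (Predictors) and potentially avoidable readmission (Development vs. validation).
- No model targets the secondary outcome, an 18-day readmission in the same major diagnostic category that leads to case merging.
- Source-country rates are 10%-15% (US) and 9%-10% (Canada).
- Only same-hospital readmissions count, which Limitations says can bias performance either way.
- Missing inputs are coded as normal or absent.
- LACE+ without the case-mix score already calibrated poorly in its internal validation.

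At stake is the stated comparison. A reader who sees one model ahead on Brier or Net Benefit could not tell how much is better prediction and how much is a luckier average level.

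**Working it through.** **Plan's own figure.** With 500 cases, the half-width for a proportion of 50% is 1.96 × √(0.5 × 0.5/500) = 4.38%, which agrees with the stated value of slightly below 4.5%. It concerns sensitivity and specificity, not calibration.

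**Assumptions.** The documents give no local rate, merged share or mean prediction, so these are assumed. The base case has logistic risk with a normal linear predictor, SD 0.85 (AUC 0.719), a mean 30-day risk of 10% and 1,000,000 simulated patients; expected scores are computed from the true risks. The merged share m is the 18-day event rate divided by the 30-day rate.

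**One model, 18-day outcome.** Let p be the 30-day risk and q = m·p the 18-day risk. Predicting p gives Brier = E[q(1−q)] + E[(p−q)²] = m·E[p] + (1−2m)·E[p²]. Since E[p(1−p)] = 0.0840, E[p²] = 0.1000 − 0.0840 = 0.0160 and Var(p) = 0.0160 − 0.0100 = 0.0060.
- At m = 40%: 0.04 + 0.2 × 0.0160 = 0.0432. No model: 0.04 × 0.96 = 0.0384.
- Break-even: m = 1/(1 + √(Var(p)/E[p²])) = 1/(1 + √(0.0060/0.0160)) = 0.62. The range is 58-67% for 30-day rates of 5-15% and AUC 0.68-0.75.

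**Two models, 18-day outcome.** A is calibrated to 30-day readmission. The 18-day risk has the same linear predictor with a lower intercept (hence 0.0425 below rather than 0.0432). B's predictor is correlated with A's so that its AUC is 0.05 lower (about 0.67 vs 0.72). B's slope is 0.85 times that correlation, and its mean is set to a fraction of A's. The Net Benefit (NB) threshold t is twice the event rate: NB = TP/n − FP/n × t/(1−t). The update solves for a in mean(expit(a + logit(prediction))) = observed rate.

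| Share | B scale | Raw Brier A / B | Raw NB A / B | Updated Brier A / B | Updated NB A / B |
|---|---|---|---|---|---|
| 20% | 50% | 0.0291 / 0.0207 | −0.0134 / −0.0063 | 0.0192 / 0.0194 | 0.0025 / 0.0012 |
| 40% | 50% | 0.0425 / 0.0379 | −0.0085 / 0.0014 | 0.0371 / 0.0377 | 0.0047 / 0.0021 |
| 60% | 50% | 0.0561 / 0.0551 | 0.0006 / 0.0025 | 0.0538 / 0.0550 | 0.0067 / 0.0028 |
| 80% | 50% | 0.0699 / 0.0725 | 0.0070 / 0.0017 | 0.0694 / 0.0713 | 0.0084 / 0.0034 |
| 20% | 100% | 0.0291 / 0.0279 | −0.0134 / −0.0172 | 0.0192 / 0.0194 | 0.0025 / 0.0012 |
| 40% | 100% | 0.0425 / 0.0424 | −0.0085 / −0.0145 | 0.0371 / 0.0377 | 0.0047 / 0.0021 |

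Over shares of 20, 40 and 60% and B scales of 40, 50 and 70%, B leads on raw Brier and raw NB in all 9 cells, and A leads in all 9 after the update.

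**NRI and risk groups.** Four-group NRI from B to A, with cut-offs at 1, 2 and 3 times the event rate, still favours A in 7 of these 9 cells (+0.14 at share 40%, scale 50%). It is negative only at share 20% with scale 40% or 50% (−0.09, −0.08). If the 18-day rate sets the baseline, A's high-risk share at a 40% merged share is about 29% raw and 4% updated.

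**Primary outcome.** If predictions are r times the true risk, Brier rises by (r−1)²·E[p²]. At r = 0.9 it is 0.0841 vs 0.0840; at r = 0.5, 0.0880. For the documented AUCs of 0.743 and 0.72, Brier order reverses only if the better model is mis-scaled by more than about 31% and the other is calibrated.

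A second calculation uses the midpoints of the source-country rates as mean predictions, 12.5% for A (AUC about 0.75) and 9.5% for B (about 0.70). A leads at a local rate of 10% (0.0833 vs 0.0860). B leads at 7.5% (0.0682 vs 0.0674) and 5% (0.0536 vs 0.0490). With intercepts matched, A leads at 5% (0.0450 vs 0.0462).

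**Limit of the update.** At a 40% share, if the 18-day and 30-day linear predictors correlate at only 0.7, AUC is 0.659, updated Brier is 0.0380 (no model 0.0384, true risk 0.0371) and the calibration slope is 0.69. The update does not repair a different ranking; the slope reveals it.

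**Hosmer-Lemeshow.** The same 15% over-prediction is flagged in 8%, 60% and 100% of samples at n = 1,000, 5,000 and 20,000. O/E is 1/1.15 = 0.87 each time.

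**The case against.** Penalising miscalibration is what Brier and Net Benefit are for. The protocol asks how the models perform as supplied, before routine use; a score worse than no model would be a correct answer. AUC is reported separately and does not depend on scale. The decile plot would make a 2.5-fold over-prediction obvious, and the protocol acknowledges that Brier combines both aspects and that outcomes and capture differ. All of this stands: original-weight results are the valid external validation, and gross mis-scaling would not be hidden. It does not supply a measured size of miscalibration or a comparison free of it.

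A reader might infer three stronger claims that the documents do not support:
- *Mis-scaling also drives the ranking on NRI and risk groups.* NRI is distorted but keeps its sign in most of the cells examined. The protocol uses risk groups to classify patients, not to rank models, and names no deciding measure.
- *The problem lies mainly in the 18-day outcome.* Without local rates this cannot be said; the primary outcome could be affected or nearly untouched.
- *A reversal is to be expected.* It depends on unequal scales. A 40-50% scale fits SQLape only if it predicts avoidable readmissions, whereas Predictors says unforeseen ones.

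**Conclusion.** The gap holds: calibration is part of the protocol's own definition of external validation but is not quantified, and average shift is not separated from the Brier and Net Benefit comparison. Whether this changes a conclusion depends on figures the documents lack. Under the base assumptions, a 30-day model scores worse than no model on the 18-day Brier below a merged share of about 62%. A weaker model on 40-70% of the scale overtakes a better one at shares of 20-60%. With equal scales, Net Benefit does not reverse, and Brier reverses at a 20% share and is about tied at 40%. At an 80% share neither reverses. On the primary outcome the effect is negligible at a 10% mis-scaling, but reversal is possible at a local rate of about 7.5% or less if source-country midpoints stand for mean predictions and the model on the higher scale discriminates better. This is a cheap improvement, not an invalid design.

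**What to change.** In Statistical analysis:
1. For each model and each outcome, report O/E (or the calibration intercept) and the calibration slope with 95% confidence intervals beside the decile plot. Do not rest the calibration conclusion on the Hosmer-Lemeshow test.
2. Keep the original-model results as the external validation. Add, as a labelled secondary display, Brier and Net Benefit (and NRI and risk groups, if reported) after an intercept update for each outcome, with the logit of the predicted probability as offset.
3. Interpret between-model differences from the paired AUC difference together with original and updated results. State that the update removes only the average shift, whatever its source, and does not correct a different ranking of patients.

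No new data are needed, only a small addition in R. With 500 events among all eligible inpatients, the relative half-width of O/E is 1.96 × √((1 − rate)/500): 8.3% at a 10% rate and 8.6% at 4%. The slope's standard error of 0.054-0.060 gives about ±0.11 to ±0.12. The costs are one parameter per model and outcome estimated on the validation data, and SQLape (a Poisson model run through a plugin) must be exported as a per-patient probability.
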